2.2. Endpoints

Primary Endpoint(s)

Non-invasive break up time (NIBUT)/ non-invasive keratography break up time (NIKBUT) time in seconds

NIBUT/NIKBUT is measured as the time interval in seconds after the final blink to the first appearance of distortion in the reflected rings; or to the time that the participant has to blink due to discomfort.

Secondary Endpoint(s)

Meibomian Gland Expressibility (Appendix I)

Meibomian gland expressibility is assessed in three regions of the lower eyelid: temporal, central, and nasal. Approximately five glands are expressed per region and evaluated using a four-grade scale: 0 = No Secretion, 1 = Inspissated, 2 = Colored/Cloudy Liquid, and 3 = Clear Liquid Oil. The total score is calculated as the sum of all grades across the three regions and ranges from 0 to 45.

Conjunctival Staining

Conjunctival staining is graded and recorded by quadrant (Superior, Inferior, Nasal, and Temporal) using the following grading scale: Grade 0 = None, Grade 1 = Trace, Grade 2 = Mild, Grade 3 = Moderate, and Grade 4 = Severe. Average grade can be calculated based on grades of the four quadrants.

Lid Wiper Epitheliopathy (Appendix H)

Horizontal lid margin staining and sagittal lid margin staining are graded for each eyelid separately. The horizontal and sagittal grades are then averaged for each eyelid to obtain the upper lid average grade and lower lid average grade. The final grade is the average of the upper and lower lid average grades. Subjects can be classified according to their final grades for each eye. The classification is defined as follows: “None” for final grades of 0, “Mild” for final grades between 0.25 and 1.00, “Moderate” for final grades between 1.25 and 2.00, and “Severe” for final graded between 2.25 and 3.00.

Other Exploratory Endpoint(s)

Subjective Comfort Assessed by (0-100) Numeric Scale

Subjective comfort will be assessed using a numeric scale which ranges from 0 to 100, where 100 is defined as “Best comfort imaginable” and 0 as “Worst comfort imaginable”.

Dry Eye Symptoms Measured by CLDEQ-8 and/or DEQ-5

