2.3. Hypotheses

This is a pilot study and all the hypotheses are exploratory in nature.

Primary Hypotheses

There will be no difference between Test lens and Spectacles with respect to non-invasive break up time/ non-invasive keratography break up time among habitual contact lens wearers (the interventional arm) at 1-Week follow-up.

Secondary Hypotheses

There will be no secondary hypotheses. The following will be estimated for Test lens and Spectacles among habitual contact lens wearers at 1-Week follow-up:

- Total scores of Meibomian gland expressibility
- Average grades of conjunctival staining
- Proportions of eyes with clinically significant (Grade 3 or 4 of overall classification) lid wiper epitheliopathy

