14.2. Sample Size Justification

The plan is to enroll 70 eligible subjects with a minimum target of 60 subjects to complete the study. Of the total 60 subjects, 20 subjects will be habitual spectacle users (the observational arm) and 40 subjects will be habitual contact lens users (the interventional arm). The sample size was chosen by the project team, given that this study is to gain initial insights of the performance of Test lens compared to Spectacles among different users (habitual lens users and habitual spectacle users). Therefore, the sample size was not based on any empirical sample size calculation.

The power was calculated for testing the primary hypothesis based on the selected sample size of 40 subject in the intervention arm using a 2×2 cross-over design. The calculation was performed with a 2-sided type I error of 0.05 assuming the true difference of 2 (seconds) in NIBUT between Test lens and Spectacles using a linear mixed model-based power analysis method (Stroup, 1999; 2002). Historical data from [REDACTED] were used to obtain the overall variance of NIBUT. The overall variance of NIBUT was about 34 based on the historical data. The intra-class correlation between measurements obtained from the same subject and eye across periods was assumed to be $ICC_{eye(subj)} = 0.5$, and the intra-class correlation between measurements obtained from the same subject across eyes and periods was assumed to be $ICC_{subj} = 0.3$. The SAS procedure PROC GLIMMIX (SAS software Version 9.4) was used to perform the calculation.

Based on the calculation, if the true difference is expected to be 2 seconds in NIBUT, the sample size of 40 subjects (80 eyes) using a 2×2 crossover design has a power of 86% to test for a significant difference between Test lens and Spectacles with a two-sided type I error of 0.05.

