14.4. Level of Statistical Significance

All planned analysis for this study will be conducted with an overall type I error rate of 5%. Type I error will be controlled for multiplicity across interim analysis and final analysis.

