14.6. Secondary Analysis

Meibomian Gland Expressibility

The average of Meibomian gland expressibility Total scores will be calculated and compared between Test lens and Spectacles among habitual contact lens users (the interventional arm) at 1-week follow-up.

Conjunctival Staining

The average grades of conjunctival staining will be calculated and compared between Test lens and Spectacles among habitual contact lens users (the interventional arm) at 1-week follow-up.

Lid Wiper Epitheliopathy

The proportion of eyes with clinically significant (Grade 3 or 4 for overall classification) lid wiper epitheliopathy will be calculated and compared between Test lens and Spectacles among habitual contact lens users (the interventional arm) at 1-week follow-up.

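### Lid wiper epitheliopathy is scored per eye from 0 to 3.00 in 0.25 steps but compared only as a yes/no proportion at an undefined cut, which costs precision

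*Combined protocol and SAP*

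**What the plan says.** Section 2.2 grades horizontal and sagittal staining for each lid and averages the two within the lid. It then states: "The final grade is the average of the upper and lower lid average grades". The result is banded per eye as None (0), Mild (0.25 to 1.00), Moderate (1.25 to 2.00) or Severe (2.25 to 3.00). The bands carry no numbers.

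Section 2.3 says that there are no secondary hypotheses and that certain quantities will be estimated. The lid wiper quantity is "Proportions of eyes with clinically significant (Grade 3 or 4 of overall classification) lid wiper epitheliopathy". Section 14.6 repeats it as the Test-versus-Spectacles comparison: "The proportion of eyes with clinically significant (Grade 3 or 4 for overall classification) lid wiper epitheliopathy will be calculated and compared". No comparison of the mean or ordinal final grade appears anywhere.

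The other two secondary endpoints keep their full scale. The Meibomian total score is averaged and compared, and for staining "The average grades of conjunctival staining will be calculated and compared between Test lens and Spectacles". Section 14.6 names no model for any of the three.

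Appendix H scores each component 0 to 3, records 8 grades per subject evaluation, and notes that the grades are not averaged.

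**The concern.** Comparing lid wiper epitheliopathy between lens and spectacle wear is a named secondary objective, and Section 14.2 says the study is meant to give initial insights. Once the grade becomes a flag, only eyes that cross one threshold contribute. If the cut lies between bands, a move from 0.25 to 1.00, or from 1.25 to 2.00, counts as no change. With 40 completers, the pilot's estimate could be too imprecise to guide later work, although finer data were collected.

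The cut is also unclear. If the four bands were numbered 1 to 4, Grade 3 or 4 would mean Moderate or Severe (final grade 1.25 or above). If they were numbered 0 to 3, it would mean Severe only (2.25 or above), and Grade 4 would not exist. The only grading scale in Section 2.2 that reaches a Grade 4 is the one for conjunctival staining. As written, the proportion cannot be computed without interpretation.

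**Working it through.** **The scale.** The final grade is the sum of four 0-3 grades divided by 4. The sum runs from 0 to 12, so there are 13 possible values, 0 to 3.00 in steps of 0.25.

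**The plan's own power figure (NIBUT only).** Inputs from Section 14.2:
- alpha: "The calculation was performed with a 2-sided type I error of 0.05";
- effect: "assuming the true difference of 2 (seconds) in NIBUT between Test lens and Spectacles";
- overall variance 34;
- ICC 0.5 (same eye across periods) and 0.3 (same subject across eyes and periods).

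The variance components are subject 0.3 × 34 = 10.2, eye within subject 0.2 × 34 = 6.8, and residual 0.5 × 34 = 17. The SE of the treatment difference is √(2 × 17 / 2 / 40) = 0.652, and 2 / 0.652 = 3.07. Power is 86.6% by the normal approximation, and 84.8%, 85.8% and 86.1% by noncentral t with 38, 78 and 118 df. This agrees with the plan's statement that "the sample size of 40 subjects (80 eyes) using a 2×2 crossover design has a power of 86" percent. It is the only power figure in the documents.

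**Carrying the design to lid wiper (an assumption).** Borrow the standardised effect 2/√34 = 0.343 SD and both ICCs for a latent severity with variance 1. On the full scale the SE is √(2 × 0.5 / 2 / 40) = 0.112 SD, the ratio is 3.07 and power is 85.8% (78 df).

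Now cut that scale so that 30% of spectacle eyes are above:
- Proportion above the cut on Test: 1 − Φ(0.524 − 0.343) = 0.428, a difference of 0.128.
- Probability that the same eye is above in both periods (bivariate normal, correlation 0.5): 0.2007.
- Variance of one eye's difference: 0.30 × 0.70 + 0.428 × 0.572 − 2 × (0.2007 − 0.30 × 0.428) = 0.310.
- The covariance between the two eyes' differences is about 0.001, so the variance of a subject's two-eye mean difference is (0.310 + 0.001) / 2 = 0.156.
- SE = √(0.156 / 40) = 0.062; ratio 0.128 / 0.062 = 2.05; power 52.7%.

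As precision, the 95% CI half-width (1.99 × SE) is 0.223/0.343 = 65% of the effect on the full scale and 0.124/0.128 = 97% of it after the cut. The information retained is (2.05/3.07)² = 0.45, or about 18 of the 40 subjects.

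| Spectacle eyes above cut | Binary power | Loss from 85.8% |
|---|---|---|
| 50% | 54.5% | 31 points |
| 30% | 52.7% | 33 points |
| 20% | 46.6% | 39 points |
| 10% | 34.4% | 51 points |

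**Allowing for the coarse grade.** The table treats the full scale as perfectly continuous. A simulation closer to Section 2.2 cuts four 0-3 components from the latent value (loading 0.70 or 0.85, mean grade 0.5 to 1.55), averages them, and applies a period-adjusted crossover t-test (38 df). At 0.343 SD:
- power on the mean grade is 54-74%;
- power on the 1.25 cut is 28-48%, a loss of about 20-30 points;
- power on the 2.25 cut is 6-45%, a loss of about 26-50 points.

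A different measurement model, with one latent grade rounded to 0.25 steps, gives 76-84% on the grade and losses of 28-58 points at the 1.25 cut. The losses are largest where few eyes reach the cut.

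**Other effect sizes.** In the four-component simulation the loss at the 1.25 cut is 1-4 points at 0.10 SD and 1-6 points at 0.80 SD. In the continuous calculation, over prevalences of 5-50%, it is 5-8 points at 0.10 SD, 11-18 at 0.15 SD, 5-37 at 0.60 SD and 0.2-12 at 0.80 SD. With both ICCs set to zero at 0.343 SD it is 17-30 points (prevalences 10-50%). The share of information retained is steadier. From 0.10 to 0.80 SD the flag is worth about 17-19 of 40 subjects at 30-50% prevalence and 10-12 at 10%.

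**The case against.** **No lid wiper test exists to lose power.** This stands. Section 2.3 sets no secondary hypotheses, calls the study an exploratory pilot and speaks of estimation. Section 14.2 gives power only for NIBUT. The proper term is lost precision, and the power figures serve only as a scale for it.

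**A reader might infer that the cut always costs some 20 points or more.** The documents do not support that. They give no lid wiper inputs, and the gap depends on effect size, prevalence, correlation and measurement model. It can be close to nil.

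**A reader might also infer that a real shift would go unseen.** That is too strong. Section 14.1 provides descriptive summaries of efficacy variables as appropriate, so the grades may well be tabulated by treatment. A table is not a within-subject contrast with an interval, however.

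**The proportion of clinically significant eyes is a legitimate quantity.** Agreed, which is a reason to keep it. But no rationale is given for making it the only comparison, and its cut is undefined.

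**Appendix H says the grades are not averaged.** The conflict with Section 2.2 is real and must be reconciled. It does not block the analysis, because the 8 recorded grades are enough to derive the Section 2.2 grade for each eye.

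**A mean treats ordinal data as interval.** This stands as a limitation. The horizontal bands in Appendix H are unequal in width, and grades may pile up at 0.

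**Conclusion.** The concern holds as a point about precision. The plan defines a 13-level grade per eye and compares only a flag at a cut that its own scales do not define. On the borrowed NIBUT effect and correlations, the flag is worth fewer than half of the 40 subjects, and the illustrative power gaps in the working apply. These sizes rest wholly on assumed inputs and are not a floor. What needs no assumption is that change within a band is discarded, that lid wiper is the only secondary endpoint treated this way, and that the cut cannot be applied as labelled. For a secondary endpoint in a pilot this is a modest but cheap improvement, and it does not threaten the primary analysis.

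**What to change.** In Sections 2.3 and 14.6, make the lid wiper comparison the Test minus Spectacles difference in mean final grade per eye, with a 95% CI from the Section 14.5 crossover mixed model. That model has fixed effects for lens type, sequence, period, subject group and group-by-lens interaction, random site and subject, and correlation within eye across periods. State that the final grade is derived at analysis from the 8 recorded component grades, and reconcile Section 2.2 with the Appendix H note on averaging.

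Keep the proportion of eyes above a cut as a supporting summary. The sponsor should state that cut on the 0-3.00 scale in place of Grade 3 or 4.

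The cost is a few sentences and one more model run, with no new data, procedure or subject. There are two small downsides. A mean grade is less directly clinical, and it treats as interval data an ordinal average that may cluster at 0. The retained proportion covers the first; an ordinal model as a check would address the second.

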14.7. Other Exploratory Analyses

- Other exploratory endpoints will be analyzed descriptively to compare Test lens and Spectacles among habitual lens users (the interventional arm).
- Further comparisons will be conducted between Test lens/Spectacles for habitual lens users and Spectacles for habitual spectacle users with respect to all endpoints. The first period data from habitual lens users (the interventional arm) and all data from habitual spectacle users (the observational arm) will be used to analyze these endpoints descriptively.

14.8. Interim Analysis

No interim analysis is planned for this study.

14.9. Procedure for Handling Missing Data and Drop-Outs

Missing or spurious values will not be imputed. The count of missing values will be included in the summary tables and listings.

Subject dropout is expected to be one of the main reasons of missing data in this clinical trial. Past clinical trials don't provide the evidence that subject dropout is systematic or not-at-random. To evaluate the impact of missing data, sensitivity analysis will be conducted using multiple imputation methods if the proportion of subject dropout is greater than the 15%.

14.10. Procedure for Reporting Deviations from Statistical Plan

The analysis will be conducted according to that specified in above sections. There are no known reasons for which it is planned to deviate from these analysis methods. If for any reason a change is made, the change will be documented in the study report along with a justification for the change.

15. DATA HANDLING AND RECORD KEEPING/ARCHIVING

15.1. Electronic Case Report Form/Data Collection

The data for this study will be captured on electronic case report forms (eCRFs) using an EDC system (Bioclinica). An authorized data originator will enter study data into the eCRFs using the EDC system. Data collected on equipment that is not captured in EDC will be formatted to the specification of the JJVC database manager and sent to JJVC for analysis.

External Date Sources for this study include: Nightly text messaging comfort scores. These will be analyzed by the sponsor and included in the CSR.

The clinical data will be recorded on dedicated eCRFs specifically designed to match the study procedures for each visit. Once completed, the eCRFs will be reviewed for accuracy and completeness and signed by the Investigator. The sponsor or sponsor's representatives will be authorized to gain access to the subject recordation for the purposes of monitoring and auditing the study.

Edit checks, electronic queries, and audit trails are built into the system to ensure accurate and complete data collection. Data will be transmitted from the clinical site to a secure central database as forms are completed or updated, ensuring information accuracy, security, and confidentiality. After the final database lock, the Investigator will be provided with Individual Patient Profiles (IPP) including the full audit trail on electronic media in PDF format for all of the study data. The IPP must be retained in the study files as a certified copy of the source data for the study.

The content and structure of the eCRFs are compliant with ISO14155:2011.¹

15.2. Subject Record

At a minimum, subject record should be available for the following:

- subject identification
- eligibility
- study identification
- study discussion
- provision of and date of informed consent
- visit dates
- results of safety and efficacy parameters as required by the protocol
- a record of all adverse events
- follow-up of adverse events
- medical history and concomitant medication
- test article receipt/dispensing/return records
- date of study completion
- reason for early discontinuation of test article or withdrawal from the study, if applicable

The subject record is the eCRF or an external record. The author of an entry in the subject record must be identifiable. The first point of entry is considered to be the source record.

Adverse event notes must be reviewed and initialed by the Investigator.

16. DATA MANAGEMENT

16.1. Access to Source Data/Document

The Investigator/Institution will permit trial-related monitoring, audits, IEC/IRB review and regulatory inspection(s) by providing direct access to source data/documents. Should the

clinical site be contacted for an audit by an IEC/IRB or regulatory authority, JJVC must be contacted and notified in writing within 24 hours.

16.2. Confidentiality of Information

Information concerning the investigational product and patent application processes, scientific data or other pertinent information is confidential and remains the property of JJVC. The Investigator may use this information for the purposes of the study only. It is understood by the Investigator that JJVC will use information developed in this clinical study in connection with the development of the investigational product and therefore may disclose it as required to other clinical investigators and to regulatory agencies. In order to allow the use of the information derived from this clinical study, the Investigator understands that he/she has an obligation to provide complete test results and all data developed during this study to the Sponsor.

16.3. Data Quality Assurance

Steps will be taken to ensure the accuracy and reliability of data, include the selection of qualified investigators and appropriate clinical sites and review of protocol procedures with the Principal Investigator. The Principal Investigator, in turn, must ensure that all Sub-Investigators and clinical site personnel are familiar with the protocol and all study-specific procedures and have appropriate knowledge of the study article.

Training on case report form completion will be provided to clinical site personnel before the start of the study. The Sponsor will review case report forms for accuracy and completeness remotely during the conduct of the study, during monitoring visits, and after transmission to data management. Any data discrepancies will be resolved with the Investigator or designee, as appropriate.

Quality Assurance representatives from JJVC may visit clinical sites to review data produced during the study and to assess compliance with applicable regulations pertaining to the conduct of clinical trials. The clinical sites will provide direct access to study-related source data/documents and reports for the purpose of monitoring and auditing by JJVC and for inspection by local and regulatory authorities.

17. MONITORING

The study monitors will maintain close contact with the Principal Investigator and the Investigator's designated clinical site personnel. The monitor's responsibilities will include:

- Ensuring that the investigation is being conducted according to the protocol, any subsequent amendments, and regulatory requirements are maintained
- Ensuring the rights and wellbeing of subjects are protected
- Ensuring adequate resources, including facilities, laboratories, equipment, and qualified clinical site personnel
- Ensuring that protocol deviations are documented with corrective action plans, as applicable
- Ensuring that the clinical site has sufficient test article and supplies

- Clarifying questions regarding the study
- Resolving study issues or problems that may arise
- Reviewing of study records and source documentation verification in accordance with the monitoring plan

18. ETHICAL AND REGULATORY ASPECTS

18.1. Study-Specific Design Considerations

Potential subjects will be fully informed of the risks and requirements of the study and, during the study, subjects will be given any new information that may affect their decision to continue participation. Subjects will be told that their consent to participate in the study is voluntary and may be withdrawn at any time with no reason given and without penalty or loss of benefits to which they would otherwise be entitled. Only subjects who are fully able to understand the risks, benefits, and potential adverse events of the study, and provide their consent voluntarily will be enrolled.

18.2. Investigator Responsibility

The Principal Investigator is responsible for ensuring that the clinical study is performed in accordance with the signed agreement, the investigational plan, Section 4 of the ICH E6 guidelines on Good Clinical Practice (GCP),² and applicable regulatory requirements. GCP is an international ethical and scientific quality standard for designing, conducting, recording, and reporting studies that involve the participation of human subjects. Compliance with this standard provides public assurance that the rights, safety, and well-being of study subjects are protected, consistent with the principles of the Declaration of Helsinki 64th WMA General Assembly 2013³ and that the clinical study data are credible. The Investigator must maintain clinical study files in accordance with Section 8 of the ICH E6 guidelines on Good Clinical Practice (GCP),² and applicable regulatory requirements.

